2.4.4 Analyses of efficacy endpoints

For statistics where international and conventional units do not impact the results (eg, means and least square (LSLS) means for percent changes from baseline, p-values for both percent and absolute changes from baseline, rates of patients below a threshold), derivations will be done and statistical models will be run using conventional units. For other statistics (eg, descriptive statistics at baseline and over time, absolute changes from baseline), derivations will be done with both international and conventional units.

Figures will be provided with 2 different axes by parameter when applicable. For example, for HbA1c, figures will be presented by % and mmol/mol.

2.4.4.1 Analysis of primary efficacy endpoint(s)

2.4.4.1.1 Primary efficacy analysis

The primary efficacy variable, change in HbA1c from baseline to Week 24 in % as defined in Section 2.1.3.1 will be analyzed in the ITT population using available data during the 24-week on treatment period (defined in Section 2.1.4, used to assess the on-treatment estimand). A mixed-effect model with repeated measures (MMRM) approach will be used, under the missing at random framework carried out via SAS PROC MIXED using an adequate contrast at Visit 20 (Week 24).

The model will include fixed categorical effects of treatment group (Toujeo, Tresiba), visit (Week 8, Week 12, Week 24), treatment-by-visit interaction, randomization stratum of use of SU or meglitinides at screening (Yes, No) as well as, the continuous fixed covariates of baseline HbA1c value and baseline HbA1c value-by-visit interaction.

This model will be run with an unstructured correlation matrix to model the within-patient errors.

Parameters will be estimated using restricted maximum likelihood method with the Newton-Raphson algorithm. Denominator degrees of freedom will be estimated using Satterthwaite's approximation.

This model will provide baseline adjusted least squares (LS) means estimates at Week 24 for both treatment groups, as well as, the differences of these estimates, with their corresponding standard error (SEs) and 95% CIs.

This analysis will be performed using the randomization strata as per IVRS.

A stepwise closed testing approach will be used for the primary efficacy variable to assess noninferiority and superiority sequentially detailed in Section 2.4.4.3:

- Step 1 will proceed to assess non-inferiority Toujeo versus Tresiba. To assess noninferiority, the upper bound of the two-sided 95% CI for the difference in the mean change in HbA1c from baseline to Week 24 between Toujeo and Tresiba will be compared with the predefined non-inferiority margin of 0.3% HbA1c. Non-inferiority will be demonstrated if the upper bound of the two-sided 95% CI of the difference between Toujeo and Tresiba on ITT population is <0.3%.
- Step 2 will test superiority of Toujeo over Tresiba, only if non-inferiority of Toujeo versus Tresiba has been demonstrated. The superiority of Toujeo over Tresiba will be demonstrated if the upper bound of the two-sided 95% CI for the difference in the mean change in HbA1c from baseline to Week 24 between Toujeo over Tresiba on ITT population is <0 (zero).

The tests for the primary endpoint (Week 24) will be performed one-sided at level $\alpha = 0.025$. P-value will be provided.

Model assumption checks

The analysis of the residuals of MMRM will be based on studentized residuals. It includes:

- Normality of studentized residuals, presented graphically using histogram and QQ-plot
- Plot of studentized residuals versus predicted values.
- Distribution of studentized residuals, presented graphically using boxplots, within each category of the fixed categorical effects of the MMRM:
 - treatment group (Toujeo, Tresiba),
 - visit (Week 8, Week 12 and Week 24),
 - treatment-by-visit interaction,
 - randomization stratum of use of SU or meglitinides at screening (yes, no).

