#### **Observation period of efficacy endpoints**

The 24-week on-treatment period for efficacy endpoints (primary and secondary efficacy endpoints) is defined as the time from the first injection of open-label IMP up to 7 days after date of last IMP administration for HbA1c, 0 day for 4-point and 8-point SMPG and insulin dose, 1 day for FPG and fasting SMPG, 2 days for hypoglycemia after the last injection of open-label IMP or up to the introduction of rescue therapy, whichever is the earliest.

The randomized 24–week period for efficacy variables is defined from first dose of IMP up to Week 24, regardless of study treatment discontinuation and intake of rescue therapy.

The baseline value for efficacy endpoints is the last available value prior to the first injection of open-label IMP.

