# **11.4.2 Analyses of efficacy endpoints**

# 11.4.2.1 Analysis of primary efficacy endpoint(s)

# 11.4.2.1.1 Primary analysis

The primary efficacy variable, change in HbA1c from baseline to Week 24 in % as defined in Section 9.1.1 will be analyzed in the ITT population using available data during the 24-week on treatment period (defined in Section 9.2.1). A mixed-effect model with repeated measures (MMRM) approach will be used, under the missing at random framework carried out via SAS PROC MIXED using an adequate contrast at Visit 20 (Week 24).

The model will include fixed categorical effects of treatment group, visit, treatment-by-visit interaction, randomization stratum of use of SU or meglitinides at screening (Yes, No) as well as, the continuous fixed covariates of baseline HbA1c value and baseline HbA1c value-by-visit interaction.

This model will be run with an unstructured correlation matrix to model the within-patient errors. Parameters will be estimated using restricted maximum likelihood method with the Newton-Raphson algorithm. Denominator degrees of freedom will be estimated using Satterthwaite's approximation. This model will provide baseline adjusted least squares (LS) means estimates at Week 24 for both treatment groups, as well as, the differences of these estimates, with their corresponding SEs and 95% CIs.

A stepwise closed testing approach will be used for the primary efficacy variable to assess non-inferiority and superiority sequentially detailed in Section 11.4.2.3:

- Step 1 will proceed to assess non-inferiority Toujeo versus Tresiba. To assess noninferiority, the upper bound of the two-sided 95% CI for the difference in the mean change in HbA1c from baseline to Week 24 between Toujeo and Tresiba will be compared with the predefined non-inferiority margin of 0.3% HbA1c. Non-inferiority will be demonstrated if the upper bound of the two-sided 95% CI of the difference between Toujeo and Tresiba on ITT population is <0.3%.
- Step 2 will test superiority of Toujeo over Tresiba, only if non-inferiority of Toujeo versus Tresiba has been demonstrated. The superiority of Toujeo over Tresiba will be demonstrated if the upper bound of the two-sided 95% CI for the difference in the mean change in HbA1c from baseline to Week 24 between Toujeo over Tresiba on ITT population is <0 (zero).

The tests for the primary endpoint (Week 24) will be performed one-sided at level  $\alpha = 0.025$ .

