2.1.3 Efficacy endpoints

The baseline value for efficacy endpoints is the last available value prior to the first injection of open-label IMP.

HbA1c and FPG are measured at a central laboratory, for scheduled (see study flowchart in Table 1) and unscheduled time points.

Patients measure their SMPG using the blood glucometer and document them into the diary. The following SMPG values are copied in the eCRF (see study flowchart in Table 1).

In case of premature and permanent IMP discontinuation, patients should have a visit as soon as possible with the assessments normally planned in Visit 20 (Week 24). Afterward, the patients should continue in the study up to the scheduled date of study completion. They should be followed up according to the study procedures as specified in the protocol (except for the 7-day safety post-treatment follow-up).

In case of premature permanent IMP discontinuation or rescue therapy intake, the process described in Section 2.5.4 will be applied to retrieve efficacy assessments performed at the end of treatment visit or at pre-rescue visit.

Observation period of efficacy endpoints

- The 24-week on-treatment period (used to assess the on-treatment estimand) for efficacy endpoints (primary and secondary efficacy endpoints) is defined as the time from the first injection dose of open-label IMP up to:
 - 7 days after date of last IMP administration for HbA1c, or up to the introduction of the rescue therapy, whichever is earlier for the patient,
 - 0 day after date of last IMP administration for 4-point and 8-point SMPG and insulin dose, or up to the introduction of the rescue therapy, whichever is earlier for the patient,
 - 1 day after date of last IMP administration for FPG and fasting SMPG, or up to the introduction of the rescue therapy, whichever is earlier for the patient,
 - 2 days after date of last IMP administration for hypoglycemia or up to the introduction of rescue therapy, whichever is earlier for the patient,
- **The randomized 24–week period** (used to assess the intent-to-treat [ITT] estimand) for efficacy variables is defined from first dose of IMP up to Week 24, (visit 20), regardless of study treatment discontinuation and intake of rescue therapy.

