2.1.4 Safety endpoints

The safety analysis will be based on:

- All hypoglycemia events (according to American Diabetes Association [ADA] Workgroup on Hypoglycemia),
- Local tolerability at injection site,
- Hypersensitivity reactions,
- Adverse events with special interest (AESI) with immediate notification:
 - Increase in alanine aminotransferases (ALT);
 - Pregnancy;
 - Symptomatic overdose with IMP/NIMP;
- Other adverse events (AE) or serious adverse events (SAEs),
- Vital signs including body weight.

In case of premature permanent IMP discontinuation or rescue therapy intake, the process described in Section 2.5.4 will be applied to retrieve safety assessments performed at the end of treatment visit or at pre-rescue visit.

Observation period for safety endpoints

The observation period of safety data will be divided into 3 segments:

• **The pre-treatment period** is defined as the time between the date of the signed informed consent and the first injection of open-label IMP.

- The on-treatment period (24-week on-treatment period / 24-week TEAE period) is defined as the time from the first injection of open-label IMP up to 7 days (or 2 days for hypoglycemia) after the last injection of open-label IMP, regardless of the introduction of rescue therapy. The 7-day interval is chosen based on the half-life of the IMP (approximately 5 times the half-life of Tresiba).
 - **12-week on-treatment period (12-week TEAE period)** is defined as the time from the first injection of IMP up to Week 12 or 7 days (or 2 days for hypoglycemia) after the last injection of IMP whichever comes earlier.
- **The post-treatment period** is defined as the time starting 8 days (or 3 days for hypoglycemia) after the last injection of open-label IMP (after on-treatment period). The baseline value for safety endpoints will be the last available value prior to the first injection of open-label IMP.

The on-study observation period is defined as the time from start of treatment until the end of the study (defined as last protocol planned visit or the resolution/stabilization of all serious adverse events and adverse events with pre-specified monitoring).

The baseline value for safety endpoints will be the last available value prior to the first injection of open-label IMP.

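### The SAP's primary analysis cites the safety window, which runs past rescue, for an estimand that its own efficacy section and the protocol end at rescue

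*SAP*

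**What the plan says.** SAP 2.4.4.1.1 fits the primary mixed model for repeated measures (MMRM) to HbA1c values from the 24-week on-treatment period, "defined in Section 2.1.4, used to assess the on-treatment estimand".

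Two SAP sections define a period with that name:

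- **SAP 2.1.4 (Safety endpoints).** The period runs to 7 days (2 days for hypoglycemia) "after the last injection of open-label IMP, regardless of the introduction of rescue therapy".
- **SAP 2.1.3 (Efficacy endpoints).** The period is "used to assess the on-treatment estimand) for efficacy endpoints (primary and secondary efficacy endpoints"). For HbA1c it ends "7 days after date of last IMP administration for HbA1c, or up to the introduction of the rescue therapy", whichever comes first.

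The protocol's primary analysis (11.4.2.1.1) uses the period "defined in Section 9.2.1". The efficacy observation period given there ends a set number of days after the last injection "or up to the introduction of rescue therapy, whichever is the earliest".

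Two further rules bear on this. Protocol Section 9 keeps rescued patients on study treatment and continues their planned visits and assessments to the last scheduled visit. SAP 2.5.4 re-allocates pre-rescue assessments to the next scheduled on-site visit, but if a post-rescue value exists at that visit, the post-rescue value is used.

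**The concern.** A wrong section number is usually harmless because the target makes no sense in context. Here the target is a complete, usable definition of a period with the same name and a different rescue rule, so a programmer who follows it gets no warning.

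The affected data will exist. The rescue thresholds apply from Week 12, and HbA1c is measured again at Week 24, while rescued patients are still on study treatment. The exposed value is therefore the one used for the confirmatory contrast.

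On the literal reading, the primary analysis would also handle rescue exactly as the first key sensitivity analysis does (SAP 2.4.4.1.3, ITT estimand). The planned comparison between stopping at rescue and ignoring it would be lost.

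**Working it through.** **1. The passages side by side**

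| Place | Purpose | HbA1c after rescue |
|---|---|---|
| SAP 2.4.4.1.1, section number cited | Primary analysis | Kept (2.1.4) |
| SAP 2.4.4.1.1, estimand label | Primary analysis | Excluded (label defined in 2.1.3) |
| SAP 2.1.3 | Efficacy window, primary and secondary | Excluded |
| SAP 2.1.4 | Safety window | Not cut at rescue |
| Protocol 11.4.2.1.1 with 9.2.1 | Primary analysis | Excluded |
| SAP 2.4.4.1.3, first sensitivity analysis | ITT estimand | Kept, by design |
| SAP 2.2, completers of the on-treatment period | Disposition | Patients with rescue are not completers |

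SAP 1.5 lists the changes from the protocol's statistical section; none concerns this window. For patients who stop treatment without rescue, both SAP windows allow 7 days after the last dose, so only rescued patients are affected.

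**2. The plan's own figure**

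Inputs (Protocol 11.1, SAP 1.3): margin 0.3, SD 1.4, true difference 0, one-sided alpha 0.025, power at least 90%, 1:1 allocation.

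- n per group = 2 × 1.4² × (1.960 + 1.282)² / 0.3² = 458 after rounding up, against 460 stated.
- SE = 1.4 × √(2/460) = 0.0923.
- Power at 460 = Φ(0.3/0.0923 − 1.960) = 90.1%.

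The sample size is reproduced. Correcting the pointer does not change it.

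**3. What the literal reading could do**

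The documents give no rescue rate and no rescue effect, so both are assumed. Take the Toujeo minus Tresiba difference without post-rescue values to be exactly at the 0.3% margin, and let rescue lower Week 24 HbA1c by *b* in every rescued patient:

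- shift toward Toujeo = (rescue share on Toujeo − rescue share on Tresiba) × *b*
- chance of declaring non-inferiority = Φ(shift/SE − 1.960)

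| Rescue, Toujeo vs Tresiba | *b* (% HbA1c) | Shift (% HbA1c) | One-sided error at the margin |
|---|---|---|---|
| Equal | any | 0 | 2.5% |
| 12% vs 8% | 0.8 | +0.032 | Φ(0.347 − 1.960) = 5.3% |
| 8% vs 12% | 0.8 | −0.032 | Φ(−0.347 − 1.960) = 1.1% |
| 5% vs 2% | 0.5 / 1.0 / 1.5 | +0.015 / 0.030 / 0.045 | 3.6% / 5.1% / 7.0% |
| 10% vs 5% | 0.5 / 1.0 / 1.5 | +0.025 / 0.050 / 0.075 | 4.6% / 7.8% / 12.6% |
| 5% vs 10% | 0.5 / 1.0 / 1.5 | −0.025 / −0.050 / −0.075 | 1.3% / 0.6% / 0.3% |

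**4. Interaction with the re-allocation rule**

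Suppose a pre-rescue HbA1c is re-allocated to Week 24 and a post-rescue HbA1c is also recorded there. SAP 2.5.4 uses the post-rescue value. If the primary model then excludes post-rescue data, the patient can be left with no Week 24 value, although a valid pre-rescue one was taken. Correcting the section number alone does not prevent this.

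**The case against.** The strongest reply is that the intent is plain. The parenthesis that cites 2.1.4 also names the on-treatment estimand, and of the two window definitions only 2.1.3 carries that label and covers the primary endpoint. Section 2.1.4 is written for safety data and does not list HbA1c. The protocol, the contrast with the first sensitivity analysis, the completer definition and the absence of any listed change all point to stopping at rescue. The SAP also cites 2.1.3 correctly for the responder analyses. SAP 2.4.4.1.1 contains another misdirected pointer: it sends the closed test to 2.4.4.3, whereas multiplicity is in 2.4.4.4. This suggests careless numbering, not a choice.

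That reply stands as to intent. A reader might infer that the SAP, as written, puts post-rescue HbA1c into the primary test; the documents do not settle on that. The reply does not remove the contradiction, because two rules in force (the cited section and the 2.5.4 preference) still lead toward post-rescue values, and nothing in 2.4.4.1.1 excludes them. Nor is a safety window for an efficacy endpoint unthinkable here: Protocol 11.4.2.2 uses one for responder endpoints, and the SAP moved those to the efficacy window.

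A reader might also infer that the error necessarily favours non-inferiority. It does so only if Toujeo patients are rescued more. That is plausible when Toujeo is truly 0.3% worse, since HbA1c above 8.5% is one of the rescue thresholds. But the protocol expects comparable efficacy, under which a shift near zero is the natural reference. The illustration also gives every rescued patient the full effect; rescue started late would show only in part by Week 24.

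**Conclusion.** The concern holds as an internal contradiction, probably a cross-reference error, in the definition of the confirmatory data set. The evidence favours ending the primary HbA1c window at rescue, but the section cited says otherwise. If that section is followed, post-rescue Week 24 HbA1c enters the non-inferiority test.

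The effect has no fixed direction or size. It is near zero with equal rescue, anti-conservative with more rescue on Toujeo and conservative with less. With an assumed 0.8% rescue effect, 12% versus 8% rescue gives a 0.03% shift and about 5% one-sided error at the margin; the reverse gives about 1%. These figures rest on assumed rescue rates and effects, the planning SD of 1.4% and 460 analysed patients per group. They illustrate what could happen and do not predict it. Sample size and power are unaffected.

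It needs correcting because the primary test should have one reading, settled before database lock, and the two readings can give different non-inferiority results.

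**What to change.** 1. In SAP 2.4.4.1.1, replace the reference to Section 2.1.4 with Section 2.1.3, and state that HbA1c values obtained after the start of rescue therapy are excluded from the primary MMRM.
2. In SAP 2.5.4 (pre-rescue visit), state that for the on-treatment estimand the preference for a post-rescue value does not apply, so that the re-allocated pre-rescue value is kept. The preference can remain for the ITT estimand, which uses values regardless of rescue.

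The cost is one corrected pointer and two sentences in the SAP, plus a check that the programming specifications match. No new data are needed, and the sample size stays at 460 per group.

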### Penalized multiple imputation

In order to assess the impact of missing data, the change in HbA1c from baseline to Week 24 in % using HbA1c values during the randomized 24-week period (all post baseline available data), will be analyzed in the ITT population using a multiple imputation approach to account for missing data at any time points (including missing baseline, Week 8, Week 12 and Week 24) followed by the testing of treatment arms using an analysis of covariance (ANCOVA) model.

Missing data will be imputed 100 times to generate 100 complete data sets with the MI SAS procedure. For each simulation leading to negative imputed value, another value will be redrawn

for imputation using MINIMUM option of MI SAS procedure. Since in general, the missing pattern will not be monotone, a two-step approach will be used:

- Step 1: the MCMC method will be used in conjunction with the IMPUTE=MONOTONE option to create an imputed data set with a monotone missing pattern
- Step 2: using the monotone data set from Step 1, missing data will be imputed using the regression method

The imputation model for Step 1 will include the treatment group, baseline HbA1c value, as well as HbA1c values at Week 8, Week 12, and Week 24.

The imputation model for Step 2 will includes the same variables as in Step 1 with the randomization strata.

For each simulation leading to negative imputed value, another value will be redrawn for imputation using MINIMUM option of MI SAS procedure.

The imputed HbA1c value at Week 24 in the Toujeo group will then be penalized by adding 0.3% (corresponding to the non-inferiority margin) to the imputed HbA1c value whereas the imputed HbA1c in the Tresiba group will not be penalized. The change in HbA1c from baseline to endpoint will then be derived from observed and imputed (penalized or not) HbA1c value at Week 24.

The 100 complete data sets will then be analyzed using an analysis of covariance (ANCOVA) model including the fixed categorical effects of randomization stratum of screening HbA1c (< 8.0%,  $\geq 8.0\%$ ), and randomization stratum of use of SU or meglitinides at screening (Yes, No), treatment group (Toujeo, Tresiba), as well as, the continuous fixed covariate of baseline HbA1c value. The MIANALYZE procedure will then be used to generate valid statistical inferences by combining results from the 100 analyses using Rubin's formulae.

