1 OVERVIEW AND INVESTIGATIONAL PLAN

1.1 STUDY DESIGN AND RANDOMIZATION

This is a 24-week, multinational, multicenter, randomized, open-label, 2-arm parallel-group trial, Phase IV study comparing Toujeo® to Tresiba®.

The study will recruit outpatients with T2DM inadequately controlled on OADs with/without glucagon like peptide-1 (GLP-1) receptor agonist. At the end of the screening period, eligible patients will be randomized to one of two treatment groups:

- Toujeo (Insulin Glargine 300U) group
- Tresiba (Insulin Degludec 100U) group

Patients will receive in a 1:1 ratio either Toujeo or Tresiba.

A total of 920 patients (460 in Toujeo group and 460 in Tresiba group) are expected to be randomized from approximately 165 sites.

The randomization will be stratified by value of glycated hemoglobin A1c (HbA1c) obtained at the screening visit (< 8.0%; $\ge 8.0\%$) and sulphonylurea (SU) or meglitinides use before the day of screening (Yes; No).

The type and dose of antidiabetic background therapy will remain unchanged during the study, unless agents not approved in combination with insulin according to local labeling/local treatment guideline (if used, they will be discontinued at the start of the investigational medicinal product [IMP]) or identified safety concerns necessitate a reduction in dose or discontinuation of non-insulin antidiabetic drug(s).

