2.4.4.1.2 Subgroup analyses

Where appropriate for the size of a subgroup, exploratory analyses are performed on the primary endpoint to summarize the treatment effects across subgroups.

For each subgroup, the primary efficacy variable will be analyzed in the ITT population using post-baseline HbA1c data available on the 24-week on treatment period, (to assess the on-treatment estimand). A similar MMRM approach as described for primary analysis will be applied adding the corresponding subgroup factor, subgroup factor-by-treatment interaction, subgroup factor-by-visit interaction and subgroup factor-by-visit-by treatment interaction.

The subgroups will be defined by the following baseline and screening factors:

- Age group (<65 and \geq 65 years of age),
- Gender (male, female),
- Baseline BMI (<30; ≥ 30 and <35; ≥ 35 kg/m²),
- Randomization stratum of screening HbA1c (< 8.0%, $\geq 8.0\%$),
- Randomization stratum of use of SU or meglitinides at screening (yes, no),
- Number of previous non-insulin anti-hyperglycemic agent (0, 1, 2, >2),
- Previous non-insulin anti-hyperglycemic treatment at screening: GLP-1RA (yes/no),
- Previous non-insulin anti-hyperglycemic treatment at screening: DPP-4 inhibitor (yes/no),
- Previous non-insulin anti-hyperglycemic treatment at screening: SGLT-2 inhibitor (yes/no),
- Duration of diabetes ($<10, \ge 10$ years),
- Baseline estimated GFR categories (mL/min/1.73m²): (<15; [15-30[; [30-60[; [60-90[; ≥90).

If the subgroup factor is a randomization stratification factor, then the strata as per IVRS will be used.

The randomization strata of screening HbA1c and use of SU or meglitinides at screening will not be included in the model.

Least Square Means Difference versus Tresiba at Week 24 will be provided, as well as the corresponding SEs and 95% CI, within each subgroup. The significance level of the treatment-by-subgroup factor interaction term at Week 24 will also be provided for each factor for descriptive purpose. Forest plots will be provided.

Subgroups analyses using randomization strata derived as per electronic case report form (e-CRF), should be performed only if necessary (in case of high number of discrepancies between stratum as per IRT and stratum as per e-CRF) and should be considered as sensitivity analysis.

Further subgroup analyses may be performed if deemed necessary for interpretation of results.

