Missing data will be imputed 100 times to generate 100 complete data sets with the MI SAS procedure. For each simulation leading to negative imputed value, another value will be redrawn for imputation using MINIMUM option of MI SAS procedure. Since in general, the missing pattern will not be monotone, a two-step approach will be used:

- Step 1: the markov chain Monte Carlo (MCMC) method will be used in conjunction with the IMPUTE=MONOTONE option to create an imputed data set with a monotone missing pattern,
- Step 2: using the monotone data set from Step 1, missing data will be imputed using the regression method.

The imputation model for Step 1 will include the treatment group, baseline HbA1c value, as well as HbA1c values at Week 8, Week 12, and Week 24.

The imputation model for Step 2 will includes the same variables as in Step 1 with the randomization strata.

The imputed HbA1c value at Week 24 in the Toujeo group will then be penalized by adding 0.3% (corresponding to the non-inferiority margin) to the imputed HbA1c value whereas the imputed HbA1c in the Tresiba group will not be penalized. The change in HbA1c from baseline to endpoint will then be derived from observed and imputed (penalized or not) HbA1c value at Week 24.

The 100 complete data sets will then be analyzed using an analysis of covariance (ANCOVA) model including the fixed categorical effects and randomization stratum of use of SU or meglitinides at screening (Yes, No), treatment group (Toujeo, Tresiba), as well as, the continuous fixed covariate of baseline HbA1c value. The MIANALYZE procedure will then be used to generate valid statistical inferences by combining results from the 100 analyses using Rubin's formulae.

This procedure will provide baseline adjusted least-squares means estimates at Week 24 for both treatment groups, as well as, the differences of these estimates, with their corresponding SEs and 95% CIs.

Tipping point analysis

Robustness of the primary analysis results to departure from the MAR assumption will be explored in the ITT population using tipping-point analysis based on the pattern mixture model approach.

The considered pattern mixture model will introduce a sensitivity parameter, δ , corresponding to the difference in means between patients with missing data and patients with observed data.

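### The HbA1c subgroup MMRMs drop both randomization strata, and the SAP's imputation ANCOVA silently drops one that the protocol includes

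*SAP*

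**What the plan says.** **Randomization.** SAP 1.1 states: "The randomization will be stratified by value of glycated hemoglobin A1c (HbA1c) obtained at the screening visit". The cut is at 8.0%, and the second factor is SU or meglitinide use (Yes; No). Protocol 8.5 agrees.

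**Primary MMRM.** SAP 2.4.4.1.1 includes "randomization stratum of use of SU or meglitinides at screening (Yes, No) as well as, the continuous fixed covariates of baseline HbA1c value", with a baseline-by-visit interaction. Protocol 11.4.2.1.1 has the same terms: "randomization stratum of use of SU or meglitinides at screening (Yes, No) as well as, the continuous fixed covariates". Neither includes the screening-HbA1c stratum.

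**Subgroup MMRMs on the primary endpoint.** SAP 2.4.4.1.2 takes a model similar to the primary one and adds the subgroup factor and its interactions. It then says: "The randomization strata of screening HbA1c and use of SU or meglitinides at screening will not be included in the model". The list has 11 subgroup factors, and only two of them are randomization strata.

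**Hypoglycemia subgroup models.** SAP 2.4.5.1 removes a stratum when it equals the subgroup or forms part of an adjustment factor. It also allows removal if the logistic model does not converge.

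**Penalized-imputation ANCOVA.** The protocol specifies a model "including the fixed categorical effects of randomization stratum of screening HbA1c" and then names the SU/meglitinide stratum, treatment and baseline HbA1c. SAP 2.4.4.1.4 reads "including the fixed categorical effects and randomization stratum of use of SU or meglitinides at screening", with treatment and baseline HbA1c. Imputation Step 2 uses the randomization strata in both documents. The entries in SAP 1.5 concern insulin dose and the SMPG profiles; none mentions this ANCOVA.

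**The concern.** The primary model treats SU/meglitinide use as a factor to adjust for, and the trial randomizes by it. The subgroup models answer the same question within subgroups but discard it, and the SAP gives no reason. The screening-HbA1c stratum at least has a close proxy there, continuous baseline HbA1c. SU/meglitinide use has none, except where it is itself the subgroup.

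Stratified randomization balances SU use across the whole trial but not within, say, an age or BMI subgroup. Without the term, any chance imbalance there passes into the subgroup estimate and its interval is slightly wider than it need be.

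The ANCOVA is a matter of traceability. A sensitivity analysis of the primary endpoint has different covariates in the two documents. The SAP sentence reads as if a term had fallen out, so a reader cannot tell a decision from a drafting slip. The tipping-point analysis reuses the same imputation approach.

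**Working it through.** **1. The plan's own figure.** Inputs (Protocol 11.1, SAP 1.3): margin 0.3%, SD 1.4%, true difference 0, one-sided 2.5%, power 90%.

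n per arm = 2 × SD² × (z₀.₉₇₅ + z₀.₉₀)² / margin² = 2 × 1.96 × (1.960 + 1.282)² / 0.09 ≈ 458, or 916 in total. At 460 per arm, SE = 1.4 × √(2/460) = 0.0923 and power is 0.901. The stated 920 reproduces. It rests on the unadjusted SD, so no choice of covariates below changes it.

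**2. The models side by side.**

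| Model | HbA1c stratum | SU/meglitinide stratum | Continuous baseline HbA1c |
|---|---|---|---|
| Primary MMRM (protocol and SAP) | no | yes | yes |
| Penalized-imputation ANCOVA, protocol | yes | yes | yes |
| Penalized-imputation ANCOVA, SAP | no | yes | yes |
| HbA1c subgroup MMRMs, SAP | no | no | yes |
| Hypoglycemia subgroup models, SAP | unless it matches | unless it matches | not stated |

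In the HbA1c subgroup row, a stratum enters only when it is itself the subgroup factor.

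**3. Size, by simulation.** 4,000 trials per setting, N = 920, permuted blocks of 4 within the four strata, single-time-point ANCOVA, total SD of change 1.4%. The following are assumptions, not document figures: screening HbA1c normal (mean 8.7, SD 0.85) truncated to 7.5–10.5; screening–baseline correlation 0.8 or 0.9; baseline slope −0.6; SU effect 0.3% with 60% users; residual HbA1c-stratum effect 0, 0.2 or 0.4%.

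Mean SE of the treatment difference, correlation 0.8, true difference 0 (all models contain baseline HbA1c):

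| Residual HbA1c-stratum effect | Both strata | SU only | Neither |
|---|---|---|---|
| 0 | 0.0877 | 0.0877 | 0.0882 |
| 0.2% | 0.0882 | 0.0883 | 0.0888 |
| 0.4% | 0.0886 | 0.0890 | 0.0895 |

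- Dropping both strata raises the SE by 0.0005 to 0.0009 across all settings. The SU stratum alone accounts for 0.0005 to 0.0006 of this.
- Power falls by at most about 0.5 point (92.5% to 92.05%).
- The empirical SD of the estimate moves by at most 0.0002. In the whole trial, where allocation is balanced on the strata, omission mainly makes the reported SE slightly too large.

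**4. Hand check and range for the SU term.** With SU in the model, residual variance ≈ SE² × N/4 = 0.0877² × 230 = 1.769. Omitting a factor with effect d and share p adds d² × p(1 − p).

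- d = 0.3, p = 0.6: 0.09 × 0.24 = 0.0216, or 1.2% of 1.769. SE rises 0.6%, and 0.0877 × 1.0061 = 0.0882, as simulated.
- d = 0.15: 0.0054, or 0.3%. SE rises about 0.15%.
- d = 0.5: 0.06, or 3.4%. SE rises about 1.7%.

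These percentages do not depend on n, so they carry over to a subgroup with the same share of users. There SU use is not balanced by design, so the loss is real. With 100 per arm (illustrative), the SD of the between-arm difference in SU share is √(2 × 0.24/100) = 0.069. Times 0.3, that is 0.021% HbA1c, against a subgroup SE of √1.769 × √(2/100) = 0.188. This is the same 1.2% of variance seen from another side.

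**5. The screening-HbA1c stratum in the primary model.** Adding it changes the SE by at most 0.0004 (0.0890 to 0.0886; variance ratio (0.0886/0.0890)² = 0.991) under the largest assumed residual effect. A separate simulation (400 trials of 920 per scenario, within-patient HbA1c SD 0.15 to 0.4) gave variance ratios of 0.9966 to 1.0003. Power changed by at most about 0.3 point, and type I error at the margin was the same within 0.1 point.

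**The case against.** The subgroup analyses are labelled exploratory, the interaction tests are descriptive, and the exclusion is stated outright. A different rule for a different endpoint is not in itself an error. All of this stands and is why the point is minor. It does not supply a reason to discard the SU term. The sentence might also be meant only for the two subgroups that are strata, since it follows the instruction about them. As written it is unconditional, and even on that reading it removes both strata rather than the matching one.

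On the ANCOVA, SAP 1.5 is confined to major changes, and one covariate in a sensitivity model may fall below that bar. That is arguable, but the incomplete SAP sentence still needs repair.

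Three stronger readings are tempting and not supported:

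- *The primary MMRM is defective because it lacks the screening-HbA1c stratum.* Continuous baseline HbA1c, with its visit interaction, is in the model, and protocol and SAP agree. The FPG and SMPG models and the logistic models, which carry the stratum, list no continuous baseline HbA1c term, so the division looks deliberate.
- *A gap between the primary and the imputation analysis is blurred by different covariates.* Under the SAP their baseline covariates match; the mismatch is in the protocol. The two analyses differ anyway in estimand (on-treatment against the randomized 24-week period) and in the 0.3% penalty.
- *All the other MMRMs carry both strata.* Week 12 HbA1c, both key sensitivity MMRMs and the e-CRF-stratum rerun use the primary model, and the SAP's body-weight model refers to it.

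**Conclusion.** The point holds as a small, nearly free improvement. The HbA1c subgroup MMRMs leave out a factor that the trial randomizes by and the primary model uses. Keeping it would narrow the reported SE by well under 1% at the assumed SU effect of 0.3%, and by about 1.7% at 0.5%, and would guard against chance imbalance within subgroups. The sizes come from a whole-trial, single-time-point model with assumed SU effect and prevalence; the documents give neither these nor subgroup sizes.

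The ANCOVA discrepancy between protocol and SAP is a documentation gap with negligible numerical effect. Nothing here bears on the sample size or on the validity of the non-inferiority test. Adding the screening-HbA1c stratum to the primary MMRM is optional: the variance effect was within about 0.3% in one simulation, and about 0.9% in the other under the largest residual stratum effect assumed.

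**What to change.** - **SAP 2.4.4.1.2:** replace the blanket exclusion. Keep the IVRS strata, at least SU/meglitinide, in every subgroup MMRM, and drop only the stratum that defines the subgroup. Cost: SAP wording and one or two degrees of freedom out of about 900.
- **SAP 2.4.4.1.4:** rewrite the ANCOVA sentence so that its terms are complete, reconcile it with the protocol, and record the decision in SAP 1.5. Keep its covariates matched to the primary MMRM. The simplest route is to confirm the SU-only version and list it as a change. Restoring the HbA1c stratum in the ANCOVA alone would create a mismatch, so if it is restored, add it to the primary MMRM as well.
- **Primary MMRM:** no change is needed. If the sponsor chooses to add the stratum, the protocol's primary model changes too, which costs more than SAP wording and should be documented as such.
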